# 2. Trial Objectives

Objectives	Outcome Measures	Timepoint(s) of evaluation of this outcome measure (if applicable)						
Primary Objective								
To determine if treatment with very low dose dexamethasone facilitates the extubation (for more than 24 hours) of ventilator dependent preterm babies of less than 30 weeks' gestation who are at high risk of developing BPD.	Time to first extubation after first IMP dose when the baby remains extubated for more than 24 hours.							
Secondary Objectives								
To determine if the treatment of ventilator dependent preterm babies of less than 30 weeks' gestation who are at high risk of developing BPD with very low dose dexamethasone impacts upon:								
1. Time to first extubation (whether or not more than 24 hours)	Time to first extubation after first IMP dose (whether or not more than 24 hours)							
2. Extubation by day 7	

(a) Extubation by day 7 (where the baby has remained extubated for more than 24 hours)

(b) Extubation by day 7 (whether or not more than 24 hours)

	Day 7						
3. Survival to 36 weeks' postmenstrual age	Alive at 36 weeks' PMA (or discharge home if sooner)	36 weeks' PMA (or discharge home if sooner)						
4. Respiratory morbidity to 36 weeks' PMA	(a) Total duration of invasive ventilation	36 weeks' PMA (or discharge home if sooner)						

Objectives	r					
(or discharge home if sooner)	through endotracheal tube  (b) Total duration of non-invasive respiratory support through nasal CPAP, nasal ventilation or high flow oxygen therapy  (c) Open-label treatment using local unit policy i.e. escalation of corticosteroid therapy or requirement for repeated courses of corticosteroid.  (d) Use of diuretics using local unit policy  (e) Total duration of supplemental oxygen therapy  (f) Severity of BPD at 36 weeks' PMA (or discharge home if sooner) as defined in Appendix 1. Oxygen requirement will be determined using the oxygen reduction test (see Appendix 2).					

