#### 7. Statistical Considerations

#### 7.1. Sample Size / Power Calculations

For the primary outcome of time to extubation, assuming 90% power and two-sided 5% level of significance, a log rank test with a sample size of 70 babies (35 in each arm) would be required to detect a HR of 2.3 when the control group hazard rate is 1.0. This HR is the lower end of the confidence interval found by our retrospective study; adjusted HR 6.24 (95% CI 2.34 to 16.63). This sample size will allow the detection of a clinically important absolute risk reduction of 36% for the secondary outcome of failure to extubate by day 7, with 90% power, a two-sided 5% level of statistical significance, and a control group incidence of 80%, (consistent with control group event rates reported in previous trials). As other previously published randomised trials of dexamethasone report failure to extubate by day 7 as a primary outcome, we consider this an important secondary outcome to consider in the sample size calculations.

Since all centres routinely collect the required data we anticipate a negligible loss to follow-up. However, as the primary analysis will be per-protocol, babies will be censored for the primary outcome (and other time-to-event outcomes) if the baby either dies, discontinues treatment before extubation, or remains intubated at day 16 (last day of the intervention period). These babies will be excluded from the analysis of other secondary outcomes.

Studies and published data sets show that 13.5–18% of babies <30 weeks' gestational age will have late onset sepsis, 2,18 7% will be treated for NEC,1 and 14% will be treated for PDA with cyclooxygenase inhibitors. We estimate that a third of late onset sepsis, half of NEC and a quarter of treated PDA would occur in the study period. We therefore expect that up to 14% of babies will permanently discontinue the study treatment for clinical reasons. We estimate that 10% of babies will either die before extubation, or remain intubated at day 16. These deaths will be reported to the DMC who will monitor for any safety imbalances or differences in censoring rates between the groups. The per-protocol analysis will therefore censor or exclude approximately 23% of all babies giving a final overall sample size target of at least 90 babies.

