### 7.3. Statistical Analysis

Demographic factors, clinical characteristics, and service utilisation will be summarised with counts (percentages) for categorical variables, mean (standard deviation (SD)) for normal distributed variables or median (interquartile or other percentile range) for other continuous variables.

Comparative statistical analysis will entail calculating the HR plus 95% confidence interval (CI) for the primary outcome, the risk ratio (plus 95% CI) for dichotomous outcomes, and mean or median difference (plus 95% CI), for other continuous variables. Since this is an efficacy study, for the primary analysis, babies will be analysed on a per-protocol basis, excluding babies who are discontinued from the study treatment. For the primary outcome events will be censored for babies who discontinue or die before extubation or who remain intubated at day 16.

A secondary analysis will analyse all outcomes on an intention-to-treat basis. The consistency of the effect of dexamethasone will be explored to see whether it is of particular help to specific subgroups of babies, using the statistical test of interaction. The following pre-specified subgroups will be examined for the primary outcome (1) gestational age, (2) singleton vs. multiple pregnancy and (3) diuretic use at trial outset.

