# 16. Appendices

## 16.1. Appendix 1: Severity Based Diagnostic Criteria for BPD

Time point of assessment: 36 weeks' PMA		
Therapy with oxygen > 21%		
and/or		
respiratory support for ≥ 28 days cumulatively		
and		
the following levels of oxygen requirement as determined by the oxygen reduction test		
Mild BPD	Baby is breathing room air	
Moderate BPD	Baby is in 22–29% oxygen, or 0.01–1.0 l/min	
Severe BPD	Baby is in $FiO_2 \ge 0.3$ or low flow oxygen $\ge 1.1$ l/min or the baby is receiving respiratory support (invasive or non-invasive) to achieve saturations of $\ge 91\%$	

The need for oxygen will be determined by the oxygen reduction test. This is based on the minimum inspired oxygen threshold at which the baby can maintain saturations of  $\geq$  91%. Babies requiring inspired oxygen to maintain saturations of  $\geq$  91% are considered to be oxygen dependent.

The test only applies to babies in < 0.3 inspired oxygen, or low flow oxygen of < 1.1 l/min, and who have not had respiratory support in the previous 24 hours. Those babies not meeting these criteria will not be tested, but their oxygen requirements captured on the relevant data form.

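### BPD severity has no level for death and no composite with death is defined, so the BPD comparison is conditional on survival and can be biased if mortality differs between arms

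*Protocol*

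**What the plan says.** Section 2, item 4(f) defines the outcome as "Severity of BPD at 36 weeks' PMA (or discharge home if sooner) as defined in Appendix 1". Appendix 1 grades it mild, moderate or severe from the oxygen or respiratory support the baby needs; the lowest grade is "Baby is breathing room air". The appendix states "Time point of assessment: 36 weeks' PMA" and does not repeat the allowance for earlier discharge. Neither place has a level for death. Survival to the same time point is a separate secondary outcome (Section 2, item 3).

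Section 7.1 fixes part of the handling of deaths. For the per-protocol analysis, which is the primary one, "babies will be censored for the primary outcome (and other time-to-event outcomes) if the baby either dies, discontinues treatment before extubation, or remains intubated" (the cut-off for the last of these is day 16). It then says: "These babies will be excluded from the analysis of other secondary outcomes". BPD severity is one of those other outcomes.

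Section 7.3 adds: "A secondary analysis will analyse all outcomes on an intention-to-treat basis". It names a risk ratio for dichotomous outcomes. It does not say how a baby who died before grading enters the BPD comparison.

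**The concern.** A comparison of BPD grade among graded babies compares groups formed after randomisation. If dexamethasone changes mortality, the surviving groups differ in make-up, and a difference in BPD can appear, or a real one can shrink, with no change in any individual baby's lungs. The per-protocol rule selects further. It removes babies still intubated at day 16, who are plausibly at high risk of severe BPD, and so selects on the primary outcome itself.

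Prevention of BPD is the stated indication (Study Summary), and Section 1.2 says the respiratory morbidity data are to help plan the next step in evaluating this treatment. A BPD estimate that cannot be read without knowing the mortality pattern is a weak input to that decision.

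**Working it through.** **What the plan's own figures give.** Section 7.1 expects up to 14% of babies to discontinue, and states: "We estimate that 10% of babies will either die before extubation, or remain intubated at day 16". Combined, 1 − 0.86 × 0.90 = 22.6%, which matches the stated 23% or so. Of 94 babies, 0.23 × 94 ≈ 22 would be censored or excluded per protocol. The 10% mixes deaths with prolonged intubation. The protocol gives no mortality to 36 weeks and no expected BPD rate for this population, so the rest uses assumed inputs.

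**Set-up.** Let mP and mD be mortality on placebo and dexamethasone (assumed 5–20%), b the BPD rate in babies who would survive on either arm, and q the BPD rate in the extra survivors of the lower-mortality arm. Assume no true effect on BPD, so b is the same in both arms. When mD < mP:

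Survivors-only RR = {[(1 − mP)·b + (mP − mD)·q] / (1 − mD)} / b

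**Lower mortality on dexamethasone**

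| mP v mD | b | q | Calculation | RR |
|---|---|---|---|---|
| 20% v 10% | 0.35 | 1.0 | (0.28 + 0.10)/0.90 ÷ 0.35 | 1.21 |
| 20% v 10% | 0.65 | 1.0 | (0.52 + 0.10)/0.90 ÷ 0.65 | 1.06 |
| 10% v 5% | 0.35 | 1.0 | (0.315 + 0.05)/0.95 ÷ 0.35 | 1.10 |
| 10% v 5% | 0.65 | 1.0 | (0.585 + 0.05)/0.95 ÷ 0.65 | 1.03 |
| 20% v 10% | 0.50 | 0.9 | (0.40 + 0.09)/0.90 ÷ 0.50 | 1.09 |
| 20% v 10% | 0.50 | 0.5 | (0.40 + 0.05)/0.90 ÷ 0.50 | 1.00 |
| 20% v 10% | 0.50 | 0.3 | (0.40 + 0.03)/0.90 ÷ 0.50 | 0.96 |

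**Higher mortality on dexamethasone.** The placebo arm now holds the extra survivors.
- At 10% v 20% with q = 1, RR = 0.35/0.422 = 0.83 for b = 0.35, and 0.65/0.689 = 0.94 for b = 0.65.
- At 10% v 15% with b = 0.50, RR is 0.50/0.522 = 0.96 for q = 0.9 and 0.50/0.489 = 1.02 for q = 0.3. A spurious benefit therefore needs the babies lost to have been the more severe ones.

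**A real benefit.** Take the RR of 0.76 for BPD quoted in Section 1.1 as the effect in babies who survive on either arm, with b = 0.50 and q = 0.9.
- 10% v 5%: (0.90 × 0.38 + 0.05 × 0.9)/0.95 ÷ 0.50 = 0.81.
- 20% v 10%: (0.80 × 0.38 + 0.10 × 0.9)/0.90 ÷ 0.50 = 0.88.

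**If all randomised babies stay in the denominator and an ungraded baby counts as free of BPD.** Death is then scored as a good outcome. At 20% v 10%, with the same BPD risk b in all survivors, RR = 0.90b/0.80b = 1.125.

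**Death or BPD in all randomised babies, at 20% v 10%.**
- With q = 1 both arms have 0.80b + 0.20, so RR = 1.00.
- With q = 0.8 the dexamethasone arm has 0.80b + 0.18, so RR = 0.46/0.48 = 0.96 (b = 0.35) or 0.70/0.72 = 0.97 (b = 0.65).

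**Against sampling error.** Assume 15% mortality, so about 47 × 0.85 ≈ 40 survivors per arm. The SE of log RR at RR 1 is √[2(1 − b)/(40b)]. For b = 0.65 it is 0.164, giving a 95% interval of about 0.73–1.38. For b = 0.35 it is 0.305, giving about 0.55–1.82. Every shift above lies inside the interval for its b; for the b = 0.50 rows, all lie within the narrower of the two.

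**The case against.** The strongest reply is that how deaths enter the analysis of one secondary component is ordinary SAP content, and that listing survival and BPD as separate outcomes at one time point is coherent and shows any mortality difference openly. This stands in part: the SAP may contain a rule for the intention-to-treat analysis. It does not cover what the protocol itself fixes, namely a scale without death and a written per-protocol exclusion. Showing survival beside BPD reveals a mortality difference but does not correct the BPD contrast. Read literally, Section 7.1 also takes deaths before extubation out of the per-protocol survival outcome.

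It is also fair that Section 7.3 neither dichotomises BPD grade nor limits the denominator to survivors. But the other simple denominator, all randomised babies with the ungraded counted as free of BPD, has the worse property shown above.

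The top figure, 1.21, is a corner case: mortality halved, every extra survivor with BPD, and only 35% BPD in the rest. The 35% in Section 1.1 refers to all surviving babies born before 30 weeks, whereas this trial enrols ventilated babies on at least 30% oxygen. At b = 0.65 the shift is 1.03–1.06.

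Finally, a composite is no neutral remedy. With q = 1 it reports no effect although mortality has halved. That objection stands and shapes the fix.

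**Conclusion.** The point holds as a limitation of the outcome definition and of the per-protocol exclusion. The BPD comparison is conditional on survival, and in the per-protocol analysis also on extubation and treatment continuation. It can be biased if mortality differs. With no true BPD effect and lower mortality on dexamethasone, the survivors-only RR is about 1.03–1.21 if all extra survivors have BPD, 1.00 if they resemble the others, and below 1 if they have milder disease. It also falls below 1 if mortality is higher on dexamethasone and the babies lost would have had worse BPD. All of this rests on assumed mortality of 5–20% and assumed BPD rates, and the shifts are likely to be smaller than the sampling error of a 94-baby trial.

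A reader might infer more: that a survival benefit will appear as BPD harm. The documents do not support that. It needs both a mortality difference and worse BPD in the extra survivors, and the protocol gives no figure for either. In the cases worked above, a real benefit of 0.76 is diluted to 0.81–0.88, not reversed. Nor is grading confined to babies still in hospital at 36 weeks, since Section 2 grades earlier discharges at discharge. The change is a cheap improvement and not a correction on which the trial depends.

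**What to change.** In Section 2, item 4(f), and Section 7.3:
- Add for the intention-to-treat analysis the outcome of death before 36 weeks' PMA (or discharge home if sooner) or moderate/severe BPD, in all randomised babies, as a risk ratio with 95% CI.
- State that the Section 7.1 exclusion does not apply to this contrast.
- Always show death and BPD grade separately beside it.
- Keep the graded outcome, and label BPD grade among survivors as conditional on survival.

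While editing, align the time point in Appendix 1 with Section 2 for babies discharged early.

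The cost is wording only. Survival and BPD grade are already collected, and Section 4.7 keeps data collection going after trial medication stops. The downside is that a composite mixes outcomes of different gravity and can hide a mortality effect, which is why it should be added to the graded outcome without replacing it and never shown without its components.

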### Secondary outcomes

- Time to first extubation after first IMP dose (whether or not more than 24 hours)
- Extubation by day 7\* (where the baby has remained extubated for more than 24 hours)
- Extubation by day 7\* (whether or not more than 24 hours)
- Survival to 36 weeks' PMA
- Markers of respiratory morbidity to 36 weeks' PMA (or discharge if sooner), as listed in protocol
- · Safety outcomes to 36 weeks' PMA (or sooner if discharged home), as listed in protocol
- · Parent/family experience

CTT01\_v13.0\_100922

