5. Safety outcomes	
 
a.) Hypertension
 
b.) Hyperglycaemia
 
c.) Confirmed/suspected sepsis
 
d.) Spontaneous gastrointestinal perforation or NEC (definitive and/or complicated (Bell stage II and above) confirmed by radiography and/or histopathology or requiring surgery)
 
e.) Deterioration in cranial ultrasound findings.
 
A new finding of severe IVH (grade III/IV with
 
	During administration of IMP and for 14 days after last dose of intervention (a-d)  CrUSS performed prior to randomisation (or when occurring according to standard clinical				

Objectives	Outcome Measures	Timepoint(s) of evaluation of this outcome measure (if applicable)
	bleeding) or new PVL on the CrUSS performed at 36 weeks' PMA (+/- 2 weeks) when compared to the scan performed most recently prior to randomisation  f.) Growth	practice) and at 36 weeks' PMA (+/- 2 weeks, or discharge home if sooner). Weight measured at trial entry, on day 14 (after randomisation) and 36 weeks' PMA (+/- 2 weeks, or discharge home if sooner)
	i) Change in standard deviation score (SDS) for weight between study entry and day 14 after randomisation.	
	ii) Change in standard deviation score (SDS) for weight between day 14 after randomisation and 36 weeks' PMA (or discharge home if sooner)	
	ii) Change in standard deviation score (SDS) for head circumference (as measured by occipito-frontal circumference) between study entry and 36 weeks' PMA (or discharge home if sooner)	Head circumference measured at trial entry, and at 36 weeks' PMA (+/- 2 weeks, or discharge home if sooner)
6. Parent/family experience	Parent/family experience: Measures of the parents'/family's hands on involvement in their baby's care.  (a) Duration, frequency and amount of contact with their baby  (b) Degree of parental/family involvement in cares (nappy changes, skin care, etc.)	Log recorded during 16-day intervention period. Although part of the consent process, this is not part of the source dataset and is optional for parents and staff to complete

Objectives	Outcome Measures	Timepoint(s) of evaluation of this outcome measure (if applicable)					
Exploratory Objective							
Cytokine profile	Changes to the inflammatory cytokine profile	Endotracheal tube secretions and blood					

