# 5. Investigational Medicinal Product

## 5.1. Dosing and Administration

Dexamethasone (Hospira, dexamethasone 3.3 mg/ml solution for injection) will be supplied as a clear sterile solution at a concentration of 3.3 mg per 1 ml in 2 ml vials. Cartons containing 14 single-use vials will be provided. Each carton will be labelled with a unique code and in compliance with the guidance given in Annexe 13 of the European Commission's guidelines for Good Manufacturing Practice.

Doses of 50 mcg/kg (0.015 ml/kg of 3.3 mg/ml solution) of dexamethasone will be administered daily on days 1 to 10 after randomisation (10 doses) then alternate days on days 12, 14 and 16, making a total of 13 doses. Doses are to be calculated on the current working weight of the baby at the time of randomisation (or may be increased in line with current working weight as per local practice) and diluted to appropriate volume with dextrose or saline. Current working weight will be that which is designated by individual units as the weight to manage IMPs with. While the baby has an intravenous line in situ (peripheral or central) each dose is to be given as a short intravenous infusion over 10–15 minutes. Once the baby has had intravenous access removed the IMP may be given via the nasogastric tube or orally. The dose should be prepared and diluted in the same manner for oral, nasogastric and intravenous administration.

All 13 doses will be given unless there are adverse effects necessitating stoppage, as referenced in Section 4.7. Placebo will be supplied as a clear sterile solution of 0.9% saline solution for injection. Cartons identical to those for dexamethasone, each containing 14 identical single-use vials will be provided. Volume of IMP to be withdrawn from the vial will be calculated following the calculations for dexamethasone dosing and then diluted with dextrose or normal saline for administration.

Following randomisation, first dose should be administered after the necessary baseline data collection. Once the vial is opened the drug must be used immediately.

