### 6.3. Recording SAEs

Non-serious adverse events will not be routinely recorded as the IMP is well-studied in this age group with fairly extensive reporting of safety outcomes in systematic reviews. Also, the IMP is a licenced product which is being given at a much lower dose than the standard dose for neonates. However, adverse events which are part of the safety outcomes of the trial will be recorded in the CRF. SAEs as described in this section will be monitored from randomisation until 14 days after last dose of treatment with the IMP and recorded on the CRF.

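### The lead safety analysis is per-protocol, so babies whose sepsis or NEC ends treatment can drop out of the comparison meant to count those events

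*Protocol*

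**What the plan says.** Section 2, objective 5, lists six safety outcomes. For (a) hypertension, (b) hyperglycaemia, (c) confirmed or suspected sepsis and (d) perforation or NEC, the period is "During administration of IMP and for 14 days after last dose of intervention (a-d". Cranial ultrasound (e) and growth (f) are assessed up to 36 weeks' PMA. The Trial Flow Diagram gives one line for the whole set: "Safety outcomes to 36 weeks' PMA (or sooner if discharged home), as listed in protocol".

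On the analysis population, Section 7.3 says that "for the primary analysis, babies will be analysed on a per-protocol basis, excluding babies who are discontinued from the study treatment", with intention-to-treat for all outcomes as a secondary analysis. Section 7.1 lists babies who die, who discontinue before extubation or who are still intubated at day 16. They are censored for time-to-event outcomes, and then "These babies will be excluded from the analysis of other secondary outcomes".

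Section 7.1 takes published rates of late-onset sepsis, NEC and treated PDA, assigns a share of each to the study period, and concludes: "We therefore expect that up to 14% of babies will permanently discontinue the study treatment for clinical reasons". Section 4.7 sets out when trial medication stops and requires data collection to continue afterwards.

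**The concern.** A safety comparison should not remove a baby because the baby had the safety event. Here the exclusion criterion (stopping trial medication) is, by the protocol's own account, partly caused by outcomes (c) and (d). If dexamethasone raised the risk of sepsis or perforation, the affected babies could stop treatment and leave the lead table, and the excess would be understated. Section 1.1 already expects gastrointestinal side effects from corticosteroids, and the stated aim in Section 1.2 covers safety as well as efficacy. Section 7.3 justifies the per-protocol choice on the ground that this is an efficacy study; that reason does not carry over to safety.

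The last-dose window raises a separate, smaller question. How long a baby is observed depends on when treatment stopped, which happens after randomisation and may differ between arms.

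**Working it through.** **1. The protocol's own figures (Section 7.1).**
- Sepsis in the study period: 13.5/3 to 18/3 = 4.5% to 6.0%.
- NEC in the study period: 7/2 = 3.5%.
- Treated PDA in the study period: 14/4 = 3.5%.
- Sum: 11.5% to 13.0%, against the stated ceiling of 14%.
- Combined with 10% dying or still intubated: 1 − 0.86 × 0.90 = 22.6%, the stated 23%.
- Sample size: 70/0.77 = 90.9, consistent with the stated target of at least 90.

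**2. Safety cases open to exclusion.**
- Sepsis plus NEC: 4.5 + 3.5 = 8.0% to 6.0 + 3.5 = 9.5%.
- Of 94 babies: 94 × 0.080 = 7.5 to 94 × 0.095 = 8.9.
- All exclusions under Section 7.1: 94 × 0.23 = 21.6 babies.

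If every such case did stop treatment, Section 7.3's exclusion would leave none of them in the lead table, in either arm and whatever the true difference.

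**3. Who is excluded depends on the section.** Section 7.3 removes all babies who discontinue. Section 7.1 removes only those who discontinue before extubation, but adds deaths and babies intubated at day 16. Sepsis or NEC that ends treatment after extubation is therefore excluded under 7.3 and kept under 7.1.

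**4. Length of the window for (a) to (d).** Section 5.1 schedules daily doses on days 1 to 10, "then alternate days on days 12, 14 and 16, making a total of 13 doses".
- Completer: 16 + 14 = day 30.
- Last dose on day 5: 5 + 14 = day 19.
- Last dose on day 10: 10 + 14 = day 24.

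**5. Size of the window effect.** Assume a constant event rate and that all expected discontinuers (94 × 0.14 = 13.2 babies) stop on day 5. The 30-day risk is not given, so a range is used.
- 30-day risk 18%: 1 − 0.82^(19/30) = 11.8%; shortfall 6.2 points; 13.2 × 0.062 = 0.8 events.
- 30-day risk 6%: 1 − 0.94^(19/30) = 3.8%; shortfall 2.2 points; 13.2 × 0.022 = 0.3 events.

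**6. Flow chart against Section 2.** Time from randomisation to 36 weeks' PMA:
- Born at 29 weeks 6 days, enrolled on day 24: PMA 33 weeks 2 days, leaving 19 days.
- Born at 24 weeks 0 days (an illustrative gestation), enrolled on day 10: PMA 25 weeks 3 days, leaving 74 days.

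The two end points can therefore differ in either direction from a completer's day 30.

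**The case against.** The strongest reply is that nothing is lost. Section 7.3 plans an intention-to-treat analysis of every outcome, Section 4.7 keeps data collection going after a stop, and the DMC reviews safety data (Section 6.8). That stands: a reader might infer that treatment-ending sepsis and NEC disappear from the trial, and the documents do not support this. What remains is that the table named as primary is the one with the exclusions.

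A reader might also infer that the last-dose window lets these cases escape. It does not. An event that ends treatment occurs during dosing or within 14 days of the last dose, so it falls inside the window; only the exclusion can remove it. The window and the exclusion also hardly overlap. Under Section 7.3 the lead analysis contains no discontinuers, so unequal observation belongs mainly to the intention-to-treat analysis. Section 7.1's wording could leave in a few babies who stop after extubation.

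Nor is every case excluded. Section 4.7 names overwhelming sepsis and clinician judgement, whereas outcome (c) includes any confirmed or suspected sepsis. The 7.5 to 8.9 babies come from a planning allowance.

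The flow chart is a summary that points to the protocol's list, and its 36-week limit is right for (e) and (f). The last-dose window also matches the SAE period in Section 6.3, "SAEs as described in this section will be monitored from randomisation until 14 days after last dose of treatment with the IMP", so it looks deliberate. Both points stand, and make the mismatch a minor alignment.

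Finally, an unseen statistical analysis plan may define a safety population. It would still have to depart from what Sections 7.1 and 7.3 state.

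**Conclusion.** The concern holds as a fault in which safety analysis leads. As written, the lead analysis excludes discontinuers and, under Section 7.1, also deaths and babies still intubated at day 16, about 23% in all. Up to about 7.5 to 9 of 94 babies with sepsis or NEC could leave it. That figure assumes that every study-period case stops treatment and is excluded, so it is an upper figure. The direction of any bias depends on how stopping differs between arms, which cannot be known in advance.

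The unequal window is secondary: about 0.3 to 0.8 events, on an assumed 30-day risk of 6% to 18%, a constant rate and all stops on day 5. The flow-chart difference affects (a) to (d) only. This should be fixed. It does not undermine the trial, because the data are collected and an intention-to-treat analysis is planned. No sample size change follows.

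**What to change.** In Sections 7.1 and 7.3, state that safety outcomes are analysed primarily in all babies who received at least one dose, by allocated arm, with no exclusion for discontinuation, death or continued intubation. A per-protocol safety table can remain as supportive.

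In Section 2, give outcomes (a) to (d) one observation window counted from randomisation, the same for every baby whether or not trial medication was stopped. Day 30 is a natural choice: it equals the completers' window and matches the day 17–30 column in the Section 4.1 schedule. Add a rule for babies who die or go home before it ends. Amend the flow-chart line so that 36 weeks' PMA applies only to (e) and (f).

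The cost is wording, plus a few more days of CRF entry for babies who stop early. Section 4.7 already requires their data to be collected.

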#### 6.4. Reporting Foreseeable Serious Adverse Events

The following are serious adverse events that could be reasonably anticipated to occur in this population of infants during the course of the trial or form part of the outcome data. They do not require reporting by the trial centres as SAEs but do require relevant data to be captured in the CRF:

- Death (unless cause not anticipated in this population)
- Necrotising enterocolitis or gastrointestinal perforation
- Bronchopulmonary dysplasia (or chronic lung disease as these are the same)
- Intracranial abnormality (haemorrhage or focal white matter damage) on cranial ultrasound scan or other imaging
- Pulmonary haemorrhage
- Pneumothorax
- Anaemia requiring blood transfusion
- Hyperbilirubinaemia
- Hyperglycaemia
- Coagulopathy requiring treatment
- Hypotension
- Hypertension
- Impaired renal function
- Patent ductus arteriosus (PDA)
- Retinopathy of prematurity
- Sepsis
- Fractures
- Clinically significant liver failure
- Clinically significant left ventricular hypertrophy on echocardiography
- Hydrocephalus

Only if these events are thought to be causally related to the IMP would they require urgent reporting to the trial centre as outlined in Sections 6.5 and 6.7.

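### Safety outcome 5(e) counts a new severe IVH or PVL only if it is on the 36-week or discharge scan, so lesions imaged earlier in babies who then die, or seen only on an interim scan, are left out of the comparison between arms

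*Protocol*

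**What the plan says.** The objectives table in protocol section 2 defines safety outcome 5(e), deterioration in cranial ultrasound findings, by comparing two scans. The haemorrhage part begins "A new finding of severe IVH (grade III/IV with" and goes on to require bleeding. The white-matter part is "new PVL on the CrUSS performed at 36 weeks' PMA (+/- 2 weeks) when compared to the scan performed most recently prior to randomisation".

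The timepoint column gives the first scan as "CrUSS performed prior to randomisation (or when occurring according to standard clinical" practice, and the second as "and at 36 weeks' PMA (+/- 2 weeks, or discharge home if sooner). Weight measured at trial entry" (the last words start the next item, on growth). Discharge home is named as an alternative endpoint for the second scan. Death is not.

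Outcomes (a) to (d) in the same row are handled differently. They are counted over a window: "During administration of IMP and for 14 days after last dose of intervention (a-d".

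Section 6.4 lists, among foreseeable serious events whose data must be recorded in the CRF, "Intracranial abnormality (haemorrhage or focal white matter damage) on cranial ultrasound scan or other imaging". Section 6.3 runs SAE monitoring from randomisation to 14 days after the last dose. Section 6.8 has the data monitoring committee (DMC) review these data. No section links the 6.4 data to outcome 5(e).

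**The concern.** Outcome 5(e) records a lesion's presence at one late time, not its occurrence since randomisation. Two groups of babies with a documented new lesion are therefore not cases: those who die before the second scan, and those whose lesion was seen only on a scan in between.

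The first group matters more, because it needs no clinical premise about how lesions evolve. The protocol expects deaths. Survival to 36 weeks is a secondary outcome, death is on the foreseeable list in section 6.4, and section 7.1 says "We estimate that 10% of babies will either die before extubation, or remain intubated at day 16".

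Section 1.1 gives concern about neurological harm as the reason for looking at lower doses, and section 1.2 says there is no definitive evidence of safety. An outcome meant to inform that question should not drop lesions that were imaged after treatment began.

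**Working it through.** The plan states no figure for this outcome, so there is none to reproduce. The check has three parts.

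**1. Which lesions count under the definition as written**

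| Baby | New severe lesion imaged after randomisation? | Counted in 5(e)? |
|---|---|---|
| Survives; lesion present on the 36-week or discharge scan | yes | yes |
| Survives; lesion seen on an interim scan only | yes | no |
| Dies before the second scan; lesion on earlier imaging | yes | no |

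The intention-to-treat analysis in section 7.3 does not change the last row. It brings the baby back into the population, but there is still no second scan on which the outcome could be met. The per-protocol rule in section 7.1 separately excludes babies who die before extubation from the other secondary outcomes.

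**2. Time between entry and the second scan**

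Inputs: entry at 10 to 24 postnatal days (section 3.1); last dose on day 16 (section 5.1); SAE monitoring for 14 further days (section 6.3), so to day 16 + 14 = 30. The gestations below are examples within the under-30-weeks criterion.

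- Born at 24+0 (assumed): entry at 25+3 to 27+3 weeks' PMA. The interval to 36+0 is 10 weeks 4 days to 8 weeks 4 days, or 10.6 to 8.6 weeks. SAE monitoring ends at 29+5 to 31+5, leaving 6.3 to 4.3 weeks before 36+0.
- Born at 29+6 (the oldest eligible): entry at 31+2 to 33+2. The interval to 36+0 is 4.7 to 2.7 weeks.

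The gap is therefore long for the least mature babies and short for the most mature. The scan window of 2 weeks either side moves each interval by up to that amount.

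**3. How many babies could be affected**

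Mortality to 36 weeks is not stated. The 10% in section 7.1 combines death before extubation with remaining intubated at day 16, so it cannot be used as a death rate. Over an assumed range:

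- 0.05 × 94 = 4.7
- 0.10 × 94 = 9.4
- 0.15 × 94 = 14.1

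About 5 to 14 babies would have no second scan.

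To illustrate the effect on cases, let *m* be mortality, *s* the risk of a new severe lesion in survivors and *d* the risk in babies who die, with every lesion imaged at the time. The share missed through death alone is *m·d* / [(1 − *m*)·*s* + *m·d*]. All three inputs are assumptions.

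| *m* | *s* | *d* | Injured babies of 94 | Counted in 5(e) | Share missed |
|---|---|---|---|---|---|
| 5% | 5% | 30% | 5.9 | 4.5 | 24% |
| 5% | 10% | 50% | 11.3 | 8.9 | 21% |
| 10% | 5% | 30% | 7.1 | 4.2 | 40% |
| 10% | 10% | 50% | 13.2 | 8.5 | 36% |
| 15% | 5% | 30% | 8.2 | 4.0 | 51% |
| 15% | 10% | 50% | 15.0 | 8.0 | 47% |

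For example, row 3: 0.10 × 0.30 = 0.030; 0.90 × 0.05 = 0.045; 0.030 / 0.075 = 40%.

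If 25% of survivors' lesions were also no longer visible at the second scan (a further assumption), the share missed would be 41–64% over the same grid.

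**The case against.** The best defence is that a fixed second scan gives every surviving baby the same chance of detection. Unscheduled scans depend on unit practice and on how ill the baby is, and treatment can affect clinical course even under masking. This stands. It is a reason to keep the two-scan comparison as a sensitivity analysis, but it does not justify leaving out a lesion that was actually imaged.

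A second defence is that these lesions are not lost to the trial. Section 6.4 has them in the CRF, section 6.8 puts them before the DMC, and survival is reported as its own outcome. That is correct, and a reader who inferred that brain injury in babies who die goes unmonitored would be wrong. The gap is confined to 5(e), the comparison of brain imaging between arms.

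A third is that handling of deaths belongs in the analysis plan, which is not shown. A rule for deaths could well be there. The restriction to the 36-week or discharge scan, however, is in the protocol's own definition, and a rule for missing scans would not lift it.

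A fourth is that the timepoint column's mention of standard clinical practice admits interim scans. It follows the pre-randomisation scan and most naturally describes that scan, though the table is broken at this point. If it were meant to admit interim scans, the two columns would disagree and would need reconciling.

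Finally, that a bleed may have cleared by 36 weeks is a clinical premise the protocol does not quantify, and an interval above two months applies only to the least mature babies. Both limits are accepted. The gap for babies who die does not depend on either.

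**Conclusion.** The definition of 5(e) should be changed. As written, a new severe lesion counts only if it is present on the 36-week or discharge scan. A baby who dies first cannot be a case whatever earlier imaging showed, and a lesion seen only on an interim scan is not counted. This follows from the text alone.

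The size does not. At an assumed mortality of 5–15%, about 5–14 of 94 babies would have no second scan. The 21–51% of injured babies missed through death in the illustration rests wholly on assumed risks, and on each lesion having been imaged before death.

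A reader might go further and infer that the definition would hide or reverse a difference between arms, or bias it in a known direction. The documents do not support that. They give no mortality to 36 weeks and no lesion rate, in either arm. At an assumed 5% rate only about 0.05 × 94 = 4.7 cases would be expected, so the comparison is descriptive under either definition. Nor do the documents rank 5(e) as the main safety outcome: it is one of six items, though the only one based on brain imaging.

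**What to change.** Redefine 5(e) as any new grade III/IV IVH or new PVL on any clinically performed cranial imaging from randomisation up to and including the 36-week or discharge scan, or up to death if earlier, compared with the last scan before randomisation. Report it by arm in all randomised babies, using the intention-to-treat analysis that section 7.3 already provides. Keep the present two-scan comparison alongside it as a sensitivity analysis, and show by arm the number of babies who died without a second scan.

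Costs and downsides:

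- No extra scans are needed.
- The outcome wording and its derivation change.
- CRF capture of cranial imaging findings must run to 36 weeks' PMA (or discharge or death) instead of ending with SAE monitoring 14 days after the last dose. In a baby born at 24+0 this adds about 4 to 6 weeks of collection.
- The frequency of unscheduled scans varies with unit and clinical course, so detection is less uniform than with one fixed scan. The sensitivity analysis shows how far the result depends on this.
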